12.4 Early Discontinuation of Study

A participant may be discontinued from study treatment at any time if the participant or study team determines that it is not in the participant's best interest to continue. The following is a list of possible reasons for study treatment discontinuation:

1. Participant withdrawal of consent
2. Participant is not adherent with study procedures
3. Adverse event that in the opinion of the investigator would be in the best interest of the participant to discontinue study treatment
4. Protocol violation requiring discontinuation of study treatment
5. Loss to follow-up

If a participant is withdrawn from treatment due to an adverse event, the participant will be followed and treated by the Investigator until the abnormal parameter or symptom has resolved or stabilized.

All participants are free to withdraw from participation at any time, for any reason, specified or unspecified, and without prejudice.

Reasonable attempts will be made by the investigator to provide a reason for participant withdrawals. The reason for the participant's withdrawal from the study will be recorded in the study.

12.5 Withdrawal of Participants from the Study

A participant may be withdrawn from the study at any time if the participant, the sponsor/investigator, or the study team determines that it is not in the participant's best interest to continue.

All participants are free to withdraw from participation at any time, for any reason, specified or unspecified, and without prejudice.

Reasonable attempts will be made by the investigator to provide a reason for participant withdrawals. The reason for the participant's withdrawal from the study will be specified in the participant's source documents. As noted above, participants who discontinue study early (i.e., they withdraw prior to the last visit) should have an early discontinuation visit if they have been discharged from the hospital. Participants who withdraw should be encouraged to come in for a final laboratory visit.

When a participant withdraws or is withdrawn from the study, the reason(s) for withdrawal will be recorded by the investigator on the relevant page of the eCRF. These participants will be requested to complete the EOS assessments scheduled for end of participation.

12.6 Lost to Follow-up

A participant will be considered lost to follow-up if he or she repeatedly fails to return for scheduled visits without stating an intention to withdraw consent and is unable to be contacted by the study site. The following actions must be taken if a participant fails to return to the study site for a required study visit:

1. The site must attempt to contact the participant and reschedule the missed visit as soon as possible, counsel the participant on the importance of maintaining the assigned visit schedule, and ascertain whether the participant wishes to and/or should continue in the study.
2. Before a participant is deemed lost to follow-up, the investigator or designee must make every effort to regain contact with the participant (where possible, 3 telephone calls and, if necessary, a certified letter to the participant's last known mailing address or local equivalent methods). These contact attempts (e.g., dates of telephone calls and registered letters) should be documented in the participant's study source document.

3. Should the participant continue to be unreachable, he/she will be considered to have withdrawn from the study.
4. A participant should not be considered lost to follow-up until due diligence has been completed. Date of withdrawal/lost to follow-up should be the date of last contact with the participant where safety status of the participant was assessed (e.g., study site visit, telephone call).

12.7 Replacement of Participants

Any participant who is withdrawn or who is lost to follow-up from the study may be replaced at the principal investigator's discretion.

13 PROTOCOL VIOLATIONS

A protocol violation occurs when the participant, investigator, or Sponsor fails to adhere to significant protocol requirements affecting the inclusion, exclusion, participant safety and primary endpoint criteria. Protocol violations for this study include, but are not limited to, the following:

1. Failure to meet inclusion/exclusion criteria
2. Use of a prohibited concomitant medication

Failure to comply with Good Clinical Practice (GCP) guidelines will also result in a protocol violation. The Investigator will determine if a protocol violation will result in withdrawal of a participant.

When a protocol violation occurs, it will be discussed with the investigator and a Protocol Violation Form detailing the violation will be generated. This form will be signed by the Investigator. The form will be sent to the IRB and a copy will be filed in the site's regulatory binder.

14 STATISTICAL METHODS AND CONSIDERATIONS

14.1 General Considerations

Data collected in this study will be presented using summary tables and participant data listings. Continuous variables will be summarized using descriptive statistics, specifically the mean, median, standard deviation, minimum, and maximum. Categorical variables will be summarized by frequencies and percentages. Data Sets Analyzed:

- **Intent-to-Treat (ITT) Analysis Set**

The ITT analysis set includes all participants who are enrolled into a treatment (dose) group regardless of whether participants receive any study drug(s), or receive a different regimen from the regimen they were randomized to. Participants will be assigned into a dose group as described above.

- **Safety Analysis Set**

A safety analysis set will include data from participants who receive at least one dose of study treatment, with treatment assignments designated according to the actual treatment received. This analysis set will be used in the analyses of safety variables (primary endpoint) as well as study treatment administration.

- **Per-Protocol (PP) Analysis Set**

The PP analysis set includes data from participants in the ITT analysis set who meet the general criteria defining the target population for this study, are adherent to the protocol, are compliant with study drug treatment, and are evaluable for relevant efficacy endpoints. Treatment assignment will be designated according to the actual treatment received. The PP analysis set will be used in the analyses of the secondary endpoints. The PP analysis set will only include participants randomized to the dose-group (Cohorts 1 and 2, Figure 1). The PP analysis set will exclude participants in the sentinel mid-dose (n=2), sentinel high-dose (n=2) and initial standard-dose groups (n=2) who were not randomized to their dose-group. Participants who are found to have detectable anti-N-protein IgG antibody levels (representing prior infection) at their Day 1 (baseline) visit will be excluded from the PP analysis set.

14.2 Demographic and Baseline Characteristics

The following demographic variables at screening will be included: race, ethnicity, sex, age, BMI, medication history, co-morbidities including cardiovascular disease, risk factors for cardiovascular disease, and immunosuppressive agents.

14.3 Analysis of Primary Endpoint

Safety will be measured by the frequency and grade of AEs (solicited and unsolicited), SAEs, AESIs, MAAEs. Reactogenicity will be measured by the occurrence and severity of solicited injection site and systemic reactions. Simple descriptive statistics will be used to summarize toxicities in terms of type, severity and minimum or maximum values for laboratory measures, time of onset, duration, and reversibility or outcome. Tables will be created to summarize these toxicities and side effects. Safety Analyses will be performed on Safety Analysis Set.

14.4 Analysis of Secondary Endpoints

- Binding antibody:** The anti-RBD and anti-spike (S-2P) IgG concentrations (log10 and geometric mean concentrations (GMC)) at Day 30 will be evaluated with comparisons between the standard-dose versus high-dose groups. T-tests with two-sided $p<0.05$ significance will be used (overall α level of 0.1). Changes in the anti-RBC and anti-spike IgG concentrations at Day 30 will be compared between the standard-dose versus high-dose groups using two sample T-tests with two-sided $p<0.05$ significance (overall α level of 0.1). The percent of participants with detectable antibody levels (greater than the LLOQ) at Day 30 will also be evaluated using Fisher's exact tests. Pairwise comparisons of binding antibodies will also be evaluated between the standard-dose versus mid-dose groups.
- Neutralizing antibody:** Neutralizing antibody titers (geometric mean titers (GMT)) from a pseudovirus neutralization assay at Day 30 will be compared between the standard-dose versus high-dose groups using T-tests with two-sided $p<0.05$ significance (overall α level of 0.1). Changes in the neutralizing antibody titers at Day 30 will be compared between the standard-dose versus high-dose using two sample T-tests with two-sided $p<0.05$ significance (overall α level of 0.1). The percent of participants with detectable neutralizing antibody levels (greater than the LLOQ) at Day 30 will also be evaluated using Fisher's exact tests. Pairwise comparisons of neutralizing antibodies will also be evaluated between the standard-dose versus mid-dose groups.

3. **Cellular immunogenicity:** The change in the frequency of target cytokine producing T-cells by flow cytometry with intracellular staining at Day 30 will be compared using the Kruskal-Wallis Test for the standard-dose versus high-dose groups. A comparison of T-cell frequencies between the standard-dose versus high-dose groups will be evaluated using the Wilcoxon rank-sum test. Pairwise comparisons of cellular immunogenicity will also be evaluated between the standard-dose versus mid-dose groups.

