CONTROL PRODUCT, DOSE AND ROUTE OF ADMINISTRATION	The mRNA-1273 vaccine, provided as a sterile liquid at a concentration of 0.2 mg per milliliter, will be administered by injection into the deltoid muscle in a volume of 0.25 ml (50 ug), 0.5 ml (100 ug) or 1.0 ml (200 ug). Vaccine mRNA-1273 will be stored at 2° to 8°C (35.6° to 46.4°F) at clinical sites before preparation and vaccination. No dilution was required. Doses could be held in syringes for up to 8 hours at room temperature before administration.
DURATION OF PARTICIPANT PARTICIPATION AND DURATION OF STUDY	
Treatment: Day 1 intramuscular injection
 
Follow-up: 6 months
 
Participants will be on study for up to 7 months.
 
The total duration of the study for recruitment and completion of participants is expected to be up to 12 months.

CONCOMITANT MEDICATIONS	Based on inclusion criteria, participants will be required to be on a regimen of triple immunosuppression including prednisone, mycophenolate mofetil (minimum 250 mg bid) or mycophenolate sodium (minimum 180 mg bid), and tacrolimus at the Day 1 study visit. Participants receiving IVIG or augmented immunosuppression for treatment of acute cellular rejection or antibody mediated rejection will be excluded from the study.
EFFICACY EVALUATIONS	
PRIMARY ENDPOINT	
 1. Frequency and grade of each solicited local and systemic reactogenicity AE will be recorded on a daily diary using the FDA Toxicity Grading Scale and collected from Day 1 until Day 7. 2. Frequency and grade of each unsolicited adverse events will be recorded on a daily diary and collected from Day 1 until Day 30.

	
3. Frequency of any serious adverse experiences (SAEs) and adverse events of special interests (AESIs) will be collected from Day 1 until Day 180.

SECONDARY ENDPOINTS	
1. Humoral immunogenicity measured by anti-RBD and anti-spike (S-2P) IgG levels at Day 30.
 
2. Humoral immunogenicity measured by neutralizing antibody titers from a pseudovirus neutralization assay at Day 30.
 
3. Cellular immunogenicity measured by cellular response assays including flow cytometry with intracellular staining at Day 30.

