3.2 Secondary Objectives

1. Evaluate humoral immunogenicity measured by anti-RBD and anti-spike (S-2P) IgG levels at Day 30.

2. Evaluate humoral immunogenicity measured by neutralizing antibody titers from a pseudovirus neutralization assay at Day 30.
3. Evaluate cellular immunogenicity measured by cellular response assays including flow cytometry with intracellular staining at Day 30.

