4 STUDY DESIGN

4.1 Study Overview

This is a Phase I/II open-label dose-finding trial among lung transplant recipients who received three or four mRNA vaccine doses (mRNA-1273 or BNT162b2) after lung transplantation to: standard-dose (50 ug), mid-dose (100 ug) or high-dose (200 ug) mRNA-1273 booster vaccine. Participants will be enrolled into three dose groups: 1) Standard-dose (50 ug) – 20 participants, 2) Mid-dose (100 ug) – 20 participants, 3) High-dose (200 ug) – 20 participants. The first 2 participants in both the mid-dose and high dose groups will be considered the ‘sentinel’ group. Participants in the sentinel group will receive the vaccine and undergo a 7-day observation period for safety and reactogenicity before additional participants are enrolled into that dose group.

Overall study enrollment will begin with the mid-dose sentinel group (n=2). During the observation period for the mid-dose sentinel group, we will enroll two participants into the standard-dose group. Once the mid-dose sentinel group completes their 7-day observation period without triggering halting rules and is approved to proceed by the DSMB, we will enroll the next 27 participants (Cohort 1) with a 2:1 randomization into the mid-dose (n=18) and standard-dose (n=9) groups.

Once all 20 participants have received their mid-dose vaccine without triggering halting rules and is approved to proceed by the DSMB, we will enroll the high-dose sentinel group (n=2). Once the high-dose sentinel group completes their 7-day observation period without triggering halting rules and is approved to proceed by the DSMB, we will enroll the next 27 participants (Cohort 2) with a 2:1 randomization into the high-dose (n=18) and standard-dose (n=9) groups. Thus, all 20 participants in the mid-dose group will be enrolled prior to enrollment of the high-dose group.

We will perform stratified randomization for the two cohorts based on: 1) the number of prior doses, and 2) prior receipt of any BNT162b2 vaccines. Randomization will be done by the UCLA Clinical and Translational Science Institute (CTSI) statistics team based on scheduled participants prior to the study visit. The 6 participants in the sentinel (n=4) and initial (n=2) groups (Table 1) will be assigned into the 3 groups based on their scheduled visit day.

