10.2 Visit 1 Day 1 (Clinic): Booster Vaccine Day

1. For participants who meet inclusion/exclusion criteria, the investigator team will again review the study with the participant (or participant's legal representative) in person and obtain written informed consent and HIPAA authorization.
2. Record demographic data.
3. Record medical history.
4. Review of birth control history with female participants of childbearing potential (<1 year since start of menopause).

5. For women of childbearing potential, counsel participants to use adequate birth control methods required during the trial to avoid pregnancy.
6. For women of childbearing potential, urine pregnancy test will be checked prior to study drug administration on Visit 1 (Day 1).
7. Confirmation participants meet all inclusion criteria and no exclusion criteria review.
8. Review pre-study concomitant medications and therapies and record on the appropriate CRF.
9. Review of influenza and any all 2019-CoV vaccinations or other experimental coronavirus vaccines.
10. Vital signs (HR, BP, temperature, oximetry), and height and weight for determination of BMI.
11. Full physical exam will include assessments of the following organs and organ systems: skin, head, ears, eyes, nose, and throat (HEENT), neck, lungs, heart, liver, spleen, abdomen, extremities, lymph nodes (axillary and cervical), and nervous system.
12. Obtain blood samples for baseline: Total immunoglobulins (IgG, IgA, IgM), anti-RBD, anti-spike binding and neutralizing antibody levels, PBMCs collected for cellular response assays including flow cytometry with intracellular staining, whole blood collected for cellular response assays, troponin / CK and cytokines for storage.
13. Confirm group assignment: standard-dose, mid-dose or high-dose group.
14. Inform participants of their designated dose.
15. Administration of booster vaccine.
16. Participants will be observed for 30-minutes post injection administration.
17. Dispense daily diary of symptoms for first 7 days after injection dispensed to participant measuring FDA Toxicity Grading Scale and adverse events.

10.3 Visit 2 Day 3 +/-1 Day (Phone – 2 days post booster):

1. All participants will complete a daily diary of solicited and unsolicited AEs from the vaccination until 7 days post-vaccination. Reactogenicity will be measured by the occurrence of solicited injection site and systemic reactions for the first 7 days post-vaccination utilizing the FDA Toxicity Grading Scale.

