14.6 Sample Size Justification

The overall mean \log_{10} IgG increase after the third (100 ug) vaccine dose was 0.46 with standard deviation (SD) 0.63. Assuming participants have a 50% lower response to the 50 ug fourth-dose, the expected mean \log_{10} IgG increase is 0.23. Assuming participants have a 100% higher response to the 200 ug fourth-dose, their expected mean \log_{10} IgG increase is 0.91. For 80% power to detect this difference between high-dose and standard-dose groups with a SD of 0.63 for a two-sample t-test with two-sided $\alpha<0.05$ significance, the minimum required sample size is 15 per group. Thus, we will enroll 20 participants in each group. The first 2 participants in the mid and high-dose groups will be enrolled as the sentinel group to ensure an acceptable safety profile before the full group is enrolled.

If the halting criteria is triggered for the high-dose group and further enrollment of this group is not recommended by the study investigators, DSMB or IRB, the study will continue randomized enrollment into the mid-dose and standard-dose groups with a 1:2 ratio to complete the enrollment of 60 participants total. Since the expected immunogenicity difference between the mid-dose and standard-dose group is smaller, we will require more participants to detect a difference between these two groups. The 1:2 enrollment ratio into the mid-dose and standard-dose groups will even the distribution of participants into these two groups. The primary endpoint analysis for safety and reactogenicity will not be affected by a restriction of participants into the mid-dose and standard-dose groups.

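### Day 30 antibody level and change from baseline are both tested, unadjusted and unranked; naming one baseline-adjusted main analysis would be a cheap improvement

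*Combined protocol and SAP*

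**What the plan says.** The statements of the humoral endpoint differ in scope:

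- Synopsis, secondary endpoints: "Humoral immunogenicity measured by anti-RBD and anti-spike (S-2P) IgG levels at Day 30". Section 3.2 words the objective the same way: "Evaluate humoral immunogenicity measured by anti-RBD and anti-spike (S-2P) IgG levels at Day 30".
- Section 5.2, which lists the secondary immunogenicity endpoints, and 14.4 items 1 and 2 cover the Day 30 value, the change, and the percentage above the LLOQ. On level, 14.4 says the concentrations "at Day 30 will be evaluated with comparisons between the standard-dose versus high-dose groups". On change, 14.4 reads: "Changes in the anti-RBC and anti-spike IgG concentrations at Day 30 will be compared between the standard-dose versus high-dose groups using two sample T-tests" (anti-RBC presumably means anti-RBD). The level and change t-tests each use two-sided p<0.05, with an overall alpha of 0.1 that is not tied to any particular set of tests.
- Section 14.6 sizes the trial on the increase: "IgG increase after the third (100 ug) vaccine dose was 0.46 with standard deviation (SD) 0.63". Expected increases are 0.23 (50 ug) and 0.91 (200 ug), giving 15 per group.

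The secondary analyses use the per-protocol set. Section 14.1 limits it: "The PP analysis set will only include participants randomized to the dose-group (Cohorts 1 and 2, Figure 1". That leaves at most 18 per arm.

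Useful covariates are already available. Section 10.2 has "Obtain blood samples for baseline: Total immunoglobulins (IgG, IgA, IgM), anti-RBD, anti-spike binding and neutralizing antibody levels", and 4.1 has "We will perform stratified randomization for the two cohorts based on: 1) the number of prior doses, and 2) prior receipt of any BNT162b2" vaccine. Section 14.4 uses neither stratification factor, and uses baseline only by subtraction in the change score.

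**The concern.** Each antibody gets two tests of the same dose effect, and the plan does not say which one is the result. If one is significant and the other is not, the choice would be made after the data are seen, in an open-label trial.

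The two estimates differ by exactly the baseline difference between the arms. A chance baseline imbalance therefore moves them apart, and with 18 per arm such imbalance is to be expected. A model with baseline as a covariate removes the conflict, because its dose coefficient is the same whether the outcome is the Day 30 value or the change.

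**Working it through.** **Inputs.** From 14.6: mean log10 increases 0.91 and 0.23, SD of the increase 0.63, two-sided alpha 0.05, 80% power. From 14.1 and 4.1: 18 v 18 randomised. Not in the documents: the correlation ρ between baseline and Day 30 log10 values, and the Day 30 SD. I assume equal variances at the two times and bivariate normality, and show a range for ρ.

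**Step 1: the plan's own figure.** Difference = 0.91 − 0.23 = 0.68. By noncentral t with SD 0.63, power is 78.5% at 14 per group and 81.4% at 15. The stated 15 reproduces. At 18 per group the change test has 88.2% power, whatever ρ is.

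**Step 2: the level test.** With equal variances, SD(change)² = 2(1−ρ)·SD(level)², so SD(level) = 0.63/√(2(1−ρ)).

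**Step 3: the adjusted model.** Residual SD = SD(level)·√(1−ρ²) = 0.63·√((1+ρ)/2). At ρ = 0.3, 0.5, 0.7 and 0.9 this is 0.51, 0.55, 0.58 and 0.61. Power was simulated (40,000 trials, 31 residual df, strata balanced and without effect); the noncentral-t formula gives about one point more or less than that.

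**Step 4: disagreement.** In the same simulated trials at the planned effect, I counted those in which exactly one of the level and change tests was significant.

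| ρ | SD(level) | Level power | Change power | Adjusted power | Level and change disagree |
|---|---|---|---|---|---|
| 0.3 | 0.53 | 96.1% | 88.2% | 96.8% | 11.6% |
| 0.5 | 0.63 | 88.2% | 88.2% | 94.7% | 15.6% |
| 0.7 | 0.81 | 68.3% | 88.2% | 91.6% | 30.0% |
| 0.9 | 1.41 | 29.1% | 88.2% | 88.5% | 63.4% |

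The last row is extreme: it needs a Day 30 SD of 1.41 log10. The adjusted model's gain over the better of the two planned tests is 0.7, 6.5, 3.4 and 0.3 points.

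**Step 5: baseline imbalance.** For a baseline difference D between arms, the level estimate shifts by ρD, the change estimate by −(1−ρ)D, and the adjusted estimate by 0. One standard error of D is SD(level)·√(2/18).

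| ρ | One SE of D | Level shift | Change shift |
|---|---|---|---|
| 0.3 | 0.177 | +0.053 | −0.124 |
| 0.5 | 0.210 | +0.105 | −0.105 |
| 0.7 | 0.271 | +0.190 | −0.081 |

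The gap between the two estimates is D itself: 0.177/0.68 = 26% to 0.271/0.68 = 40% of the planned effect.

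**Step 6: values at the LLOQ.** Section 2 reports a 59% response after dose three in the site's cohort. Assume that 100 − 59 = 41% of baselines sit at the LLOQ, and keep the observed mean changes at 0.23 and 0.91 with SD 0.63. At ρ = 0.3, 0.5, 0.7 and 0.9, adjusted power is 92.5%, 89.7%, 87.7% and 87.5%, against 88.2%, 88.1%, 88.3% and 88.4% for change. Level and change disagree in 10.0%, 13.9%, 25.2% and 52.6% of trials. The power gain nearly vanishes or turns slightly negative, while the disagreement remains.

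**Step 7: cohort.** All 18 randomised high-dose participants are in Cohort 2. Of the 18 randomised standard-dose participants, 9 are in Cohort 1 and 9 in Cohort 2. With a cohort term, high v standard rests essentially on 18 v 9: the standard-error factor rises from √(1/18+1/18) = 0.333 to √(1/18+1/9) = 0.408. Adjusted power on 18 v 9 is 88.0%, 83.1%, 78.3% and 73.7% at ρ = 0.3, 0.5, 0.7 and 0.9. A three-arm simulation with a cohort term gave 88.5%, 84.5%, 79.2% and 74.8%.

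**The case against.** **The mismatch.** A reader might infer that the trial is sized on something that is not an endpoint. The documents do not support that. Section 5.2 lists the change beside the level, 14.6 says openly that the calculation is for the increase, and the increase has its own planned test with 88% power at 18 per arm. What stands is narrower: the synopsis and 3.2 mention only the level, 5.2 and 14.4 list both, and nothing ranks them.

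**Error rate.** A reader might also infer an inflated type I error. Two tests at 0.05 match an overall alpha of 0.1, and the plan may mean this pair. The text does not say which tests the 0.1 covers, so inflation cannot be claimed. Nor does the 0.1 say which test is the main one.

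**Weight.** These are secondary endpoints in a Phase I/II trial whose primary endpoint is descriptive safety. No dose decision or success rule hangs on an immunogenicity p-value, and halting depends on safety events. This limits the point to how immunogenicity is interpreted. Still, the sample size is justified wholly on immunogenicity.

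**Power.** The gain rests on an assumed ρ and is not robust to many baselines at the LLOQ. The 41% is itself a weak guide, since participants have had three or four doses, the last at least 4 months earlier. That objection stands in full. Including a cohort term also moves power more than covariate adjustment does.

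**Completeness.** Both t-tests would still be reported and could still disagree, and the fix does not rank anti-RBD, anti-spike and neutralizing antibody or the Fisher's tests. That is true. It settles the main answer within each antibody only.

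**Conclusion.** The point holds as a low-cost improvement to a secondary analysis. Both planned tests are valid and the sample size is sound. The gap is that neither test is named as main and that baseline titre and the strata are not used as covariates. On the plan's inputs at 18 per arm, the two tests disagree in about 12% to 30% of trials for ρ from 0.3 to 0.7, and a one-standard-error baseline imbalance separates the two estimates by 0.18 to 0.27 log10.

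These sizes rest on the assumed ρ, equal variances, normality and a full 18 per arm; exclusions from the per-protocol set would reduce that number. The absence of a named main analysis depends on none of these. The case is for one pre-specified answer and correction of baseline imbalance, not for power.

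**What to change.** In 14.4 items 1 and 2, and in the matching text of 5.2 and the synopsis:

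1. Name one main analysis per antibody: a linear model of log10 Day 30 value on dose group (three levels), log10 baseline value, number of prior doses (three or four) and any prior BNT162b2 (yes or no). Report the adjusted geometric mean ratio with a 95% CI.
2. Label the level and change t-tests as supportive.
3. State the value used for results below the LLOQ.
4. State in advance whether a cohort term is included, and give the power that follows: about 74% to 88% with it (18 v 9 concurrent participants), about 89% to 97% without it, for ρ from 0.9 down to 0.3.

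The cost is wording and a few degrees of freedom. All covariates are already collected, and on these assumptions the model without a cohort term needs no more participants. The power gain over the change test may be nil or about one point negative if many baselines sit at the LLOQ.

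A smaller repair is to name one planned t-test as main; the change test is the one 14.6 sizes. That gives a single answer but leaves chance baseline imbalance uncorrected.
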